2. STUDY AIM & OBJECTIVES

Study aim

The objective of this study is to identify how influential factors change during key moments of transition during pregnancy and postpartum and to construct an intervention that effectively addresses these moments of transition to bolster ART adherence for mothers living with HIV.

Study approach

This study includes two phases:

1. A longitudinal qualitative cohort to identify and characterize factors that influence women's adherence behaviors as well as perceptions and motivations for continued treatment and engagement in care and examine participants' preferences of adherence intervention structure and delivery, in order to shape the design components of the bio-behavioral intervention.
2. Conduct an open pilot and small scale RCT of the intervention to determine feasibility, and preliminary efficacy of the intervention to improve ART adherence among pregnant and postpartum women living with HIV and in-depth interviews with intervention participants to determine acceptability and to identify ways to refine the intervention for future evaluation.

Note that Phase 1 received ethical approval from UCT HREC previously (HREC: 344/2017). This protocol focuses on Phase 2 (Aims 2 & 3).

For Phase 2, the key outcomes are:

Primary Outcomes

1. Feasibility: Feasibility will be assessed through the number of counseling sessions completed.
2. Preliminary efficacy - ART Adherence: Preliminary efficacy will be assessed as the correlation between study arm and self-reported HIV adherence on the 3 item Wilson ART adherence scale (self-report, 3 item scale recoded as 0-100, 100 indicating perfect adherence in the past month) at 6 months postpartum.
3. Preliminary efficacy- Retention in HIV services: Preliminary efficacy will be assessed as the correlation between study arm and retention in HIV services at 6 months postpartum. Retention in HIV services is measured by clinic records. Retention at 6 months postpartum is measured as attended HIV clinic appointment in the past 3 months.
4. Preliminary efficacy-viral suppression: Preliminary efficacy will be assessed as the correlation between study arm and viral suppression at 6 months postpartum. Viral suppression will be measured by clinic records, with viral suppression defined as HIV viral load less than 200 copies/mL.

Secondary Outcomes

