Our team has extensive experience in utilizing data from routinely collected electronic medical records in this setting, including for ART and PMTCT outcome assessment.^{60,61} Data will be requested from the Western Cape Provincial Data Centre, and we will use participants' provincial folder number (requested as part of tracing information) to facilitate an accurate electronic data request. Permission to review electronic clinical records of participants will be included in informed consent documents. Following standard procedures, we will request approval from the Provincial Department of Health to access electronic medical records. Established procedures are in place to ensure patient confidentiality. The project manager will link these data to participants' unique participant identifiers.

For the primary outcomes obtained from routine medical records (engagement in care and HIV viral suppression), we will use the following definitions:

- Engagement in care will be classified as any evidence of engagement in routine HIV services, including evidence of: HIV visit attendance; ART collection at a pharmacy; laboratory testing of HIV viral load or CD4 cell count
- HIV viral suppression will be classified as a viral load <200 copies/mL

For the primary outcome, we will use a window of up to 3 months around the 6-month postpartum study visit. In cases where there is evidence of multiple HIV viral load results in this window, we will use the result closest to the 6-month postpartum study visit for the primary outcome. For women who are lost to follow-up, we will use the median time of visits attended among those who are retained at study measurement visits to assess engagement in care and HIV viral suppression. As the primary outcome data will come from routine medical records, all women will have outcome data regardless of retention at study measurement visits.

Routinely collected clinical data will be linked with the written permission of (a) the participant (via informed consent), (b) the research oversight body of the Provincial Government of the Western Cape including the Provincial Data Centre, and (c) the HREC. Established procedures are in place to ensure patient confidentiality.

Aim 3 Qualitative Component

In-depth interviews will be conducted with participants randomized to the intervention condition (n=up to 30) after the completion of follow-ups in order to assess participants' experiences of the

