Sample size considerations: pilot study

The overall goal of this pilot study is to determine feasibility and potential efficacy to support future larger, fully-powered tests of the intervention's efficacy. We fully acknowledge the exploratory nature of this pilot. With a sample size of 60, between two groups, 2 follow-up measurements, controlling for self-reported baseline adherence, $p=0.05$, we will have 29% power of finding a small effect (Cohen's $d=0.30$), 65% power of finding a moderate effect ($d=0.50$), and 98% power of finding a large effect ($d=0.80$). This study will be underpowered to find significant small and moderate effects however, we will be able to calculate an effect size and the direction of its impact to support a larger scale test of the intervention.

The facility that is participating in this study, the Gugulethu MOU, sees approximately 4800 pregnant and postpartum women annually, with an antenatal HIV prevalence of 28%. Thus, we do not anticipate difficulty recruiting this sample within the allotted timeframe.

Sample size considerations: In-depth Interviews (Aim 3)

We propose to interview all of the women randomized to the intervention condition ($n=$ up to 30). Based on our follow-up rates for the longitudinal qualitative cohort (HREC 344/2017), we anticipate at least an 80% retention rate at 6 months postpartum, which equates to an anticipated 24 participants completing in-depth interviews. Based on our previous experiences working with this population, we feel that 24 participants will be enough to reach saturation on key themes related to acceptability of the intervention.

Data management

The study includes data from four sources: (1) interviewer-administered questionnaires; (2) routine electronic medical records; (3) dried blood spots; and (4) IDI with participants randomized to the intervention condition. The collection of data will be conducted by (1) a fieldworker; (2) the project manager; (3) lab-based researcher; and (4) a qualitative interviewer, respectively. Procedures for data collection (regardless of source) will be outlined in SOPs. We have a bank of well-developed SOPs that our group has developed for previous studies. All data management will take place at UCT following procedures established by our group for multiple previous studies.

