Quantitative data will be captured into a custom designed Microsoft Access database. The database will be password-protected following standard password safety procedures, and will be maintained in a firewall-protected UCT server with daily backups. The database will be designed and maintained by the project manager. The study coordinator will direct queries and data

quality assurance (QA)/quality control (QC) activities, and supervise data entry, with oversight from the project manager. Data QA will be in the form of robust database structure and platform, and 'front-end' data checks including real-time database queries. QC will be through data checking scripts to identify out-of-range values, logic violations and missing observations. Queries will be resolved based on reference to the completed questionnaires in question; all data queries and responses will be logged, and edits will be implemented through separate program files.

Qualitative data from IDI will be transcribed verbatim and translated into English. Translations will use unique participant identifiers, not participant names. All electronic files will be encrypted and password protected.

Data analysis

Quantitative data will be exported to Stata Version 14.0 (Stata Corporation, College Station, Texas) for analysis. We will analyze all primary and secondary outcomes preliminarily using simple means and standard deviations and point-biserial correlations to estimate effect sizes where appropriate. For outcomes that are indicative of a possible difference by condition, we will utilize more advanced analytic techniques, i.e generalized estimating equations (GEE), as follows:

To compare the impact of intervention condition on self-reported ART adherence, engagement in ART services and HIV viral suppression, we will utilize a series of generalized estimating equations (GEE) using Poisson distributions where appropriate. Outcome analyses will control for baseline self-reported adherence and any baseline differences on demographic variables. Intervention condition, time of assessment, and condition*time interaction will be entered as model effects. We will use GEEs to predict key psychosocial outcomes (adherence self-efficacy) by intervention condition. If there is evidence of an intervention effect we will explore factors that may modify intervention effects, we will compare intervention effects within subgroups of women based on key demographic clinical and psychosocial characteristics.

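### The named effect measure for the two yes/no primary outcomes is a correlation with arm that moves with the base rate; arm proportions and a risk difference with confidence interval are not specified, and a ratio is modelled only for outcomes that already look different

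*Combined protocol and SAP*

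**What the plan says.** Section 2 (Primary Outcomes) lists three efficacy outcomes, two of them yes/no.

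- Viral suppression: "Preliminary efficacy will be assessed as the correlation between study arm and viral suppression at 6 months postpartum". Section 7 (Linkage of routinely collected clinical data) makes it binary: "HIV viral suppression will be classified as a viral load <200 copies/mL".
- Retention: "Preliminary efficacy will be assessed as the correlation between study arm and retention in HIV services at 6 months postpartum".

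The third, the 0-100 self-reported adherence score, is also defined by its correlation with arm.

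Section 9 (Data analysis) sets out two steps. All primary and secondary outcomes are first analysed "using simple means and standard deviations and point-biserial correlations to estimate effect sizes where appropriate". Then: "For outcomes that are indicative of a possible difference by condition, we will utilize more advanced analytic techniques". The technique named is "generalized estimating equations (GEE) using Poisson distributions where appropriate", adjusted for baseline adherence and for baseline demographic differences. No threshold is given for moving to the second step, and no link function is stated.

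Section 9 (Sample size considerations: pilot study) gives the purpose of the estimate: "we will be able to calculate an effect size and the direction of its impact to support a larger scale test". For the yes/no outcomes, no risk difference, risk ratio, odds ratio or confidence interval is named anywhere.

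**The concern.** The correlation between two 0/1 variables is phi. It combines the difference between arms with the spread of the outcome, and that spread is set by the overall success rate. A reader given phi alone cannot tell a large benefit at a middling rate from a smaller benefit at a high rate. Retention and suppression may have quite different base rates, so their two correlations cannot safely be compared either.

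This matters because the larger trial will need a control proportion and a plausible difference, each with its uncertainty. The two-step rule adds a second problem. An outcome with a small first-step correlation may receive no model-based estimate. An outcome that does receive one has been chosen for looking different, so its ratio will tend to be too large.

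**Working it through.** **Inputs from the protocol.** Allocation is 1:1 (Section 7, Randomization). The planned size is 60 (Section 9), and 43 were randomized (Protocol Summary). The one base rate for a yes/no outcome is in the Introduction: 49% of women in Cape Town disengaged from care by six months postpartum, so about 51% retained. No suppression rate is given.

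**Plan's own figures.** There is none to reproduce here. The stated power (29%, 65% and 98%) is for Cohen's d of 0.30, 0.50 and 0.80, which is the scale of a continuous outcome, and does not bear on the yes/no outcomes.

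**Step 1: same benefit, different phi.** At 1:1 allocation, with RD the risk difference and pbar the average of the two arm rates, phi = RD / (2 × sqrt(pbar × (1 − pbar))). All rates below are assumed, for illustration.

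| Control vs intervention | pbar | phi | Risk ratio |
|---|---|---|---|
| 50% vs 65% | 0.575 | 0.15 / (2 × 0.494) = 0.152 | 1.30 |
| 70% vs 85% | 0.775 | 0.15 / (2 × 0.418) = 0.180 | 1.21 |
| 80% vs 95% | 0.875 | 0.15 / (2 × 0.331) = 0.227 | 1.19 |

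From the first row to the last, phi rises by about half (0.227 / 0.152 = 1.49) with the risk difference fixed at 15 points, while the risk ratio falls.

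**Step 2: same phi, different benefit.** Inverting, RD = 2 × phi × sqrt(pbar × (1 − pbar)). For phi = 0.15:

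- pbar 50%: RD = 2 × 0.15 × 0.5 = 15 points (42.5% vs 57.5%), risk ratio 1.35.
- pbar 90%: RD = 2 × 0.15 × 0.3 = 9 points (85.5% vs 94.5%), risk ratio 1.11.

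**Step 3: allocation.** With a fraction a in the intervention arm, phi = RD × sqrt(a(1 − a) / (pbar(1 − pbar))), where pbar is now weighted by arm size. For 70% vs 80%, phi is 0.115 at a = 0.50 and 0.112 at a = 0.40. Mild imbalance therefore matters little; the base rate is the main issue.

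**Step 4: the first step as a screen.** With 43 women, an observed correlation of 0.20 has a Fisher z interval of tanh(0.203 ± 1.96/sqrt(40)), which is about −0.11 to 0.47. A correlation of that size is compatible with no effect, so chance will largely decide which outcomes reach the GEE.

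**Step 5: what the fix does to precision.** For 50% vs 65% with 21.5 per arm, the Wald half-width for the risk difference is 1.96 × sqrt((0.25 + 0.2275)/21.5) = 0.29. The estimate is as uncertain as before, but it is in units that can be used.

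**The case against.** A reader might infer that the pilot will yield no usable effect size for these outcomes. The documents do not support that, for three reasons.

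- The first step also includes simple means. The mean of a 0/1 outcome is a proportion, so means by arm would give the risk difference and risk ratio.
- Section 9 names engagement in ART services and viral suppression for Poisson GEE, which with a log link gives a ratio with an interval.
- Phi can size a trial if base rate and allocation carry over. At two-sided 0.05 and 80% power (assumed), phi 0.15 needs (1.96 + 0.84)² / 0.15², about 349 in total, matching the two-proportion calculation of 174 per arm. With the pooled rate, phi converts exactly to a risk difference.

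It is also fair to say that no measure is constant under every effect model. A constant odds ratio of 2 gives 16.7 points at a 50% control rate and 8.9 at 80%. At the one base rate in the documents, 51% vs 66% gives phi 0.152, numerically almost the risk difference. The wide intervals reflect the small sample, not the choice of correlation. The pilot openly calls itself exploratory.

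All of that stands, and it limits the claim. It does not remove it. The plan never says that the means are to be read as arm proportions, nor names a difference between them as the estimate. The qualifier in "point-biserial correlations to estimate effect sizes where appropriate" does not help, because Section 2 defines efficacy by the correlation without qualification. The GEE is conditional, so it cannot be relied on to supply the missing estimate. The merit of the risk difference is not that it is invariant: reported with n/N per arm, it shows the base rate and lets the reader move to any other scale.

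**Conclusion.** The point holds in a limited form. For retention and viral suppression the plan's named effect measure mixes benefit with base rate and has no planned confidence interval. The model that could give a ratio is reserved for outcomes that already look different. For a fixed 15-point gain, phi varies from 0.15 to 0.23 across the assumed rates; near the 51% retention rate the distortion is negligible, and it grows as rates approach the high end. Whether suppression lies there cannot be judged from the documents.

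The base-rate argument does not apply to the 0-100 adherence score. The other two gaps do: no interval is planned with its correlation, and its baseline-adjusted model is conditional on the first step.

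The plan should be changed, but this is a fault in what is reported and when, not a loss of information. The data needed for the better estimate will be collected anyway.

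**What to change.** In Section 2 (Primary Outcomes) and Section 9 (Data analysis):

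- For retention and viral suppression at 6 months, report n/N per arm and the risk difference (intervention minus control) with a 95% score-type confidence interval, with the risk ratio alongside.
- For the adherence score, report the baseline-adjusted mean difference with its 95% confidence interval.
- State that these are reported for every outcome, whatever the first-step result.
- Keep the correlation as a descriptive supplement.

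The cost is a wording change to the primary outcome definitions and a few lines of code, with no new data or visits. Because it touches the primary outcome definitions and 43 women are already recorded as randomized, it should be entered as a dated change, ideally before outcomes are examined by arm. Label: free improvement.

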- Arm A (Transition theory-based intervention): Women randomized to this arm will receive monthly one-on-one meetings with a community health worker for four months during late pregnancy and early postpartum
- Arm B (enhanced standard of care): Women randomized to this arm will receive one meeting with a community health worker in addition to the local standard of care.

[figure not shown]
Women randomized to each arm will be asked to attend two additional assessment study visits at 3- and 6-months postpartum. The primary outcome will be self-reported ART adherence and secondary outcomes will be retention in routine HIV care (from routine electronic medical records) and HIV viral load using dried blood spots.

Participation will have no impact on any aspect of women's routine antenatal and obstetric care during pregnancy, or on any aspect of their postpartum care. In addition, participation will have no impact on their routine HIV care. Women randomised to the Transition intervention will receive the intervention separate from any routine medical visits. Women randomised to the enhanced standard of care will attend all routine medical visits and will receive one meeting with a community health worker separate from any routine medical visits.

Aim 3: *Assess participants' experiences of the intervention, perceived usefulness, and identify ways to refine the intervention for future evaluation.*

This aim will be accomplished using in-depth individual interviews with all participants who were randomized to the intervention condition after all follow-up assessments have been completed (n= up to 30)

The study schema is summarized in the diagram below:

Setting

The proposed study will take place in the community of Gugulethu in Cape Town. Aim 1 was successfully conducted in this community and our team has actively collaborated with local

health services in this setting for over 10 years. The antenatal HIV prevalence rate in Gugulethu is between 26-30%. Participants will be recruited during pregnancy from the Gugulethu Midwife Obstetrics Unit (MOU), which is a public sector facility that serves more than 4800 pregnant and postpartum women annually.

4. Study Population

For Phase 2 of this study (Aims 2 & 3), inclusion criteria are as follows:

- 18 years of age or older
- HIV positive status (based on clinic records)
- Confirmed pregnant (based on clinic records) and estimated to be 23-34 weeks gestation (clinic records or self-report)

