Enhanced standard of care

Women randomized to the enhanced standard of care condition will receive the local standard of care plus a one-on-one meeting with the community health worker. All antenatal services at the Gugulethu MOU follow the local standard of care. Labor and delivery take place at either the MOU or nearby obstetric hospitals. Following delivery, all women make a routine postnatal visit to the Gugulethu MOU within 7 days postpartum; this is the only form of maternal postnatal care in this setting.

HIV services are integrated into antenatal care at the Gugulethu MOU, but women are referred to their nearest ART clinic at their first postpartum clinic visit, following the local standard of care in this setting. Women attend ART visits 1-2 monthly in these services. Individual ART counselling is provided before ART initiation and again when clinicians identify adherence concerns. Infants are referred for routine infant care to local primary care clinics.

As part of the enhanced standard of care condition, participants will also receive a one-on-one session during pregnancy with the community health worker. This session will include brief education about HIV, PMTCT, and ART, brief motivation interviewing for any adherence issues, as well as a basic assessment for any necessary referrals (i.e. psychological distress, substance use issues, food insecurity).

[figure not shown]
Transition intervention/ CHW intervention

This intervention draws on Transition Theory as an overarching framework (Figure below) and was developed using data provided by participants in Aim 1 as well as an extensive literature review.

Theoretical underpinnings

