This intervention draws on the growing cadre of community health workers within the South African health care system. A recent review (Schmitz et al., 2019) of HIV specific maternal and child health programmes delivered by lay health worker in Africa found a number of strategies utilized including: community engagement and sensitization, psychosocial support, linkage to care, encouraging women to bring their infants back for HIV testing and supporting default tracing. These interventions found improvements on community awareness of mother-to-child transmission, condom use, clinic attendance/retention in care, and infant testing. However, very few of these interventions measured maternal ART adherence as an outcome.

Current South African community health worker education does not include integrated training in maternal and child health and ART adherence focused on the transition from pregnancy to postpartum. This intervention would specifically provide additional training to community health workers in this area. Furthermore, this intervention will add to the literature by measuring ART adherence as a key outcome for a community health worker-based intervention.

Proposed model

After enrollment, participants will receive monthly one-on-one sessions. During the one-on-one sessions, the CHW will utilize motivational interviewing to understand the biggest barriers to ART adherence in women's lives and to assist the women in coming up with the best strategies or approaches. These sessions will also be used to assess if any referrals need to be made such as to social services or governmental aid programs. Importantly, there is no set agenda or topical areas that must be discussed within these sessions. The topics are entirely driven by the needs of the participant.

Training for CHW

We will hire a CHW who has experience working with both pregnant/postpartum women and persons living with HIV. Training specific to this interview will take place over the course for 2 weeks. Week 1 will include training on motivational interviewing and Week 2 will focus on training in the specific topics to be covered in both the one-on-one meetings. Trainings will consist of mock intervention sessions to develop skills and provide a setting for role playing. These mock intervention sessions will be critiqued by the PI to ensure proficiency in the intervention content and consistency in delivery.

Curriculum

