A manual will be provided to the CHW. For the one-on-one sessions, the manual will describe possible areas to investigate where women may be having difficulties and information about procedures for referrals and availability of resources in the local area.

Educational materials will be adapted from the WHO and HHS/CDC Prevention of Mother-to-Child Transmission of HIV (PMTCT) Generic Training Package.⁵⁷ This training package was created as a comprehensive approach to the training of healthcare workers and provides guidelines for customized content to reflect local realities.

Process measures

The community health worker will complete logs for monitoring uptake and utilization of the intervention making note of session completion rates and dropouts. After individual sessions the CHW will also take extensive notes on topics focused on, common barriers experienced by women, and engagement within the sessions.

We will also audio record all counseling sessions to assess fidelity to the intervention. All counseling sessions will be coded using validated measures that have been adapted for this study.
 58 59

The following figure displays the differences in exposure between the Transition intervention and the enhanced standard of care as well as the assessments

| | Month 1 | Month 2 | Month 3 | Month 4 | Month 5 | Month 6 | Month 7 | Month 8 |
|--|---------|---------|--------------|--------------|--------------|--------------|--------------|--------------|
| | | | Postpartum 1 | Postpartum 2 | Postpartum 3 | Postpartum 4 | Postpartum 5 | Postpartum 6 |
| Assessments | | | | | | | | |
| Enrollment Appointment: Informed Consent, Baseline Survey Assessment, Locator Form | | X | | | | | | |
| Follow-up Quantitative Survey | | | | | X | | | X |
| Follow-up DBS | | | | | | | | X |
| Transition Intervention | | | | | | | | |
| One-on-one session with CHW | X | X | X | X | | | | |
| In-depth interviews | | | | | | | | X |
| Enhanced Standard of Care | | | | | | | | |
| One-on-one session with CHW | X | | | | | | | |

7. Study Procedures

The purpose of the study measurement visits will be to evaluate the study objectives. These study measurement visits will be carried out separately from any routine care, including antenatal, postpartum, or HIV-related care.

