Following recruitment and informed consent, all participants will be assigned unique study identification numbers. Women will complete the enrolment study visit and will then be randomized to either the Transitions intervention or control (enhanced standard of care).

Randomization

Randomization will take place at the end of the enrolment study visit. Women will be randomly allocated to either the Transitions intervention or control using a 1:1 randomization scheme. Randomization numbers will be generated prior to the start of the study and will be placed in sequentially numbered opaque envelopes. Randomization envelopes will be stored in a locked cabinet in the study office at UCT and will be accessed by the project manager when a woman is fully consented and has completed the enrolment visit. Women will be informed of their random allocation at the end of the enrolment visit. Ideally, a one-on-one meeting with the CHW (first visit for those in the Transitions intervention, only visit for those in the enhanced standard of care) would occur the same day as enrolment to aid in retention. If this is not possible the CHW will contact the participant using tracing information detailed below to inform them of the date and time of the first or only one-on-one meeting.

Quantitative measures

At each study measurement visit, a trained interviewer will administer questionnaire-based measures using paper and pencil. The trained interviewer will be blinded to participants' allocation. All study measurement visits will be conducted at a space that is separate from routine care. Most measures have been used previously by our group in this setting (see references in Table of measures, below), and have been translated into isiXhosa and back-translated into English following standard procedures. An additional scale⁴⁶ developed to measure the theoretical constructs of Transition Theory has been adapted for use with women living with HIV for this study and will be translated into isiXhosa and back-translated to English prior to use in the trial.

Linkage of routinely collected clinical data

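### Arm A sessions are meant to span delivery but are scheduled from enrolment, so the primary feasibility count can read 4 of 4 with no postpartum session

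*Combined protocol and SAP*

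**What the plan says.** Section 3 (Study Design) describes Arm A as "monthly one-on-one meetings with a community health worker for four months during late pregnancy and early postpartum". In Section 6 (Study Arms), the exposure and assessment grid has the row "One-on-one session with CHW | X | X | X | X" for the intervention. Those marks fall in Months 1 to 4, and Month 3 is headed as the first postpartum month, so two sessions precede birth and two follow it. Section 8 (Participant retention) gives 8 months of follow-up, 6 of them postpartum, which fits the same layout.

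The operational text starts from enrolment. Section 6 (Proposed model) says: "After enrollment, participants will receive monthly one-on-one sessions". Section 7 (Randomization) says the first meeting ideally "would occur the same day as enrolment to aid in retention", and otherwise: "If this is not possible the CHW will contact the participant using tracing information". Section 4 admits women "estimated to be 23-34 weeks gestation". For the control arm, Section 6 does place the contact relative to birth: "participants will also receive a one-on-one session during pregnancy with the community health worker".

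Section 2 defines the first primary outcome, feasibility, as the number of counselling sessions completed. Section 9 adds rates of attendance, retention, withdrawal and assessment completion. Neither separates sessions before delivery from those after. The primary hypothesis in Section 3 is that the intervention is feasible with postpartum women.

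**The concern.** A plan that describes sessions on both sides of delivery but schedules them monthly from enrolment gives one timetable only for women who enrol about two months before birth. The eligibility window is much wider than that. A woman enrolled early who attends every session on time could finish before she delivers and still count as full completion.

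The postpartum period is where the intervention has a specific task. Under local care, "women are referred to their nearest ART clinic at their first postpartum clinic visit", and help with linkage to care is a stated part of the community health worker's role (Section 6). If an unknown part of Arm A has no session after birth, a high completion count says little about whether sessions can be delivered then, which is something the planned larger trial would need to know. The other feasibility rates do not fill the gap. Retention and assessment completion concern measurement visits in both arms. The counselling offered to women found non-adherent at those visits (Section 7) is likewise not an intervention session.

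**Working it through.** **Inputs from the protocol.** Four monthly sessions; start at enrolment, ideally the same day; enrolment at 23-34 weeks; follow-up of 8 months with 6 postpartum.

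**Assumptions, because the protocol gives no value.** Birth week B (38-40, wider range 37-42); delay d from enrolment to first session (0, 2 or 4 weeks); a month of 365.25/12/7 = 4.348 weeks; the distribution of gestation g at enrolment.

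**1. The plan's own layout.** Two antenatal plus six postpartum months give 8, and sessions in Months 1-4 give two before and two after birth. This reproduces. It implies birth 2 × 4.348 = 8.70 weeks after enrolment, so for B = 40 it fits exactly at g = 40 − 8.70 = 31.3 weeks.

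**2. Session dates on a monthly cadence.** Sessions fall at g + d + 4.348k, k = 0 to 3. With d = 0 and B = 40:
- g = 23: 23.0, 27.3, 31.7, 36.0 (four before, none after)
- g = 28: 28.0, 32.3, 36.7, 41.0 (three before, one after)
- g = 32: 32.0, 36.3, 40.7, 45.0 (two before, two after)

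At g = 23 with no delay the last session is at 36.0 weeks, before any birth at 37-42 weeks.

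**3. Cut-off for no postpartum session.** All four sessions precede birth if g < B − d − 13.04. With d = 0 the cut-off is 24.96 weeks (B = 38), 25.96 (B = 39) and 26.96 (B = 40).

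**4. Share of women below the cut-off.** Take enrolment between 23w0d and 35w0d (34 read as completed weeks) and let u = (cut-off − 23)/12, set to 0 if negative. The share is u for even enrolment, u² for late-weighted (density proportional to g − 23) and 1 − (1 − u)² for early-weighted (proportional to 35 − g). Example for B = 40, d = 0: u = 3.96/12 = 0.330, giving 33%, 11% and 55%.

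| Delay | Even, B = 38/39/40 | Late-weighted | Early-weighted |
|---|---|---|---|
| 0 weeks | 16/25/33% | 3/6/11% | 30/43/55% |
| 2 weeks | 0/8/16% | 0/1/3% | 0/15/30% |
| 4 weeks | 0/0/0% | 0/0/0% | 0/0/0% |

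Over B = 37-42 and d = 0-4 the ranges are 0-50% (even), 0-25% (late) and 0-75% (early). If the window ends at 34w0d, the even shares with no delay become 18/27/36%. Letting birth week vary (normal, mean 39, SD 1.5, assumed) gives 25%, 8% and 42% with no delay, and 10%, 2% and 18% with a 2-week delay.

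**5. In women.** Allocating the 43 randomized women 1:1 gives about 21-22 in Arm A. At 21.5, the even, no-delay shares of 16-33% are about 3 to 7 women (21.5 × 0.163 = 3.5; 21.5 × 0.330 = 7.1).

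**6. Follow-up length.** Time from enrolment to 6 months postpartum is (B − g)/4.348 + 6 months. For B = 40 this is 9.9 at 23w0d and 7.2 at 34w6d, and equals 8 only at 31.3 weeks.

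**The case against.** The strongest reply is that the protocol does say when the sessions occur: the Arm A description and the grid both place them on each side of birth. The instruction to begin after enrolment sets no visit windows and does not forbid holding a session until after delivery. This is correct as far as it goes. A reader might infer that the intended layout is impossible across the eligibility window. The documents do not support that, because it follows only from a strict monthly cadence. What stands is that no available text says how an early enrollee's sessions are to be spaced or held back. The schema diagram and the manual might.

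Two-and-two is also a weak benchmark. It appears only in the grid, where enrolment sits in Month 2 and the first session in Month 1, so a row may have shifted in extraction. Three sessions before birth and one after still meets the Arm A description. Only women with no postpartum session bear on the concern, and that share can be zero.

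A reader might further infer that such a woman's contact differs from the control arm only by three extra antenatal sessions. That ignores content. Control women get one brief session of education, motivational interviewing and referral assessment, whereas Arm A offers participant-driven sessions and practical help with linkage, which Section 6 does not confine to the scheduled meetings. Antenatal sessions also serve the theory, which treats preparation as a transition condition.

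Finally, postpartum women in the hypothesis may be a population label, not a requirement that sessions take place after birth. That weakens the mismatch, but a total count still cannot show whether postpartum sessions are deliverable.

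**Conclusion.** The point holds as an inconsistency in scheduling and a gap in the primary feasibility outcome. The Arm A description, the grid and the follow-up length describe sessions spanning delivery, while the operational text ties them to enrolment across a wide gestational window. If the monthly cadence is followed without delay, women enrolled before about 25-27 weeks (birth at 38-40 weeks) complete all four sessions before birth, and the completion count does not reveal it.

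How many women are affected cannot be known from the documents. The shares rest on assumed birth week, delay and enrolment pattern, and a first session 4 weeks late removes the problem for births at 38-40 weeks. Confidence is therefore moderate. The finding does not show that the intervention was delivered wrongly.

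**What to change.** Report the primary feasibility outcome as sessions completed before delivery and sessions completed after delivery, alongside the total. This needs one derived variable, session date against delivery date. Delivery date is already needed to schedule the 3- and 6-month postpartum visits. Session dates may come from the community health worker's logs or the audio recordings, if these are dated, which the protocol does not state and should be confirmed. If they are, the split needs no change in conduct and can be applied to the 43 women already randomized. The counts will be small and should be presented descriptively.

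Separately, reconcile the Arm A description (Section 3), the eligibility window (Section 4), the session model and grid (Section 6), the timing of the first session (Section 7) and the follow-up length (Section 8) so that they describe one schedule. Which schedule is for the investigators to decide. If the schema figure or manual already contains a timing rule, state it in the protocol text. The cost is wording only.
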